- Severe AE drug-related in two (2) participants in one cohort;
- ECG: prolongation of QTcF to >500 ms or of >60 ms over baseline drug-related in two (2) participants in one cohort;
- Safety laboratory tests: Increase in ALT/AST ≥ 5 x ULN in 2 participants in the study;
- Safety laboratory tests: Increase in ALT/AST ≥ 3 x ULN and TBIL ≥ 2 x ULN in one (1) participant in the study;
- Other clinically significant changes in safety clinical laboratory tests, ECG, VS or other safety parameters deemed as a significant safety concern by the Investigator;
- aPTT increase > 5 x ULN at the 24h postdose time point in two (2) participants in one cohort;
- Hypersensitivity reaction occurring during study drug administration or within 6h after end of study drug administration accompanied by symptomatic bronchospasm, with or without urticaria; allergy-related oedema/angioedema; hypotension in one participant.

If no further dosing is planned due to the stopping criteria as described above, previous randomised and dosed participants will continue the study as planned. Safety assessments will be performed as planned. Pharmacokinetic assessments will be performed if deemed to be relevant and agreed by the Investigator and Sponsor without compromising the safety of a participant.

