9.7.6.2. Laboratory Safety

9.7.6.2.1. Blood safety analysis

The following parameters will be determined:

- **Haematology:**
 - Haematocrit, haemoglobin, red blood cell count, WBC count, WBC differential count, platelets counts.
- **Safety coagulation:**
 - activated Partial Thromboplastin Time (aPTT).
- **Blood chemistry:**
 - fasting glucose, creatinine, urea, sodium, potassium, calcium, chloride, phosphorus, bicarbonate.
 - AST, ALT, GGT, alkaline phosphatase.
 - total bilirubin (fraction of direct bilirubin in case > 1.25 x ULN).
 - albumin, total protein.
 - LDH, CK (and fraction of CK-MB if > 1.5 x ULN).

NB: The baseline chemistry sample (predose sample) will also contain an extra archive serum sample for anti-Borrelia serology testing as backup to test for anti-Borrelia antibodies suggestive of previous exposure to **tick bites** in case of outlying results for PK/PD.

9.7.6.2.2. *Urinalysis parameters*

The following parameters will be investigated by microscopic examination of the sediment: cylinders, erythrocytes, leucocytes.

9.7.6.2.3. *Method of assessment*

Samples of blood will be collected in fasted conditions at the visits summarised in [Section 2](#), SoA.

For all clinically significant abnormal laboratory test values identified after investigational product administration, testing will be repeated until the values return to normal or baseline. If laboratory values do not return to normal or baseline within a reasonable period, the aetiology should be identified and the Sponsor notified.

Samples of urine will be collected at the visits summarised in [Section 2](#), SoA.

9.7.6.2.4. *Laboratory safety determinations*

Laboratory tests will be performed by Clinical Biology Department of CHU of Liège, [name], Belgium.

All clinical laboratory analyses will be performed at the local laboratory. Alcohol test, urine drug screen, will be performed at the clinical site by study personnel.

Serology (HIV and Hepatitis B and C testing) will be performed only at the Screening Visit;

Urine drug screen and alcohol breath test will be performed at the Screening Visit and D-1.

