6.3. Handling of missing and retest values

No management of missing values or values below/above a limit of detection/quantification will be performed, except for pharmacokinetic values (see section 0).

For all parameters and for subjects with retest values, the last reliable value will be used for the measurement time before the study drug administration (provided it was measured before

the study drug administration) and the first reliable value will be used for the measurement time after the study drug administration.

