13.2. Clinical laboratory data

The following clinical laboratory parameters will be measured at screening, then from D1 to D4: pre-dose (D1), 24h (D2), 72h post-dose (D4), and then at the discharge visit (D10 ± 2 days) (see section 16.1).

Haematology parameters will be listed and grouped as follows:

- Red blood cells: erythrocytes ($10^{12}/L$), haematocrit (ratio), hemoglobin (g/L);
- White blood cells: basophils ($10^9/L$), basophils/leukocytes (%), eosinophils ($10^9/L$), eosinophils/leukocytes (%), leukocytes ($10^9/L$), lymphocytes ($10^9/L$), lymphocytes/leukocytes (%), monocytes ($10^9/L$), monocytes/leukocytes (%), neutrophils ($10^9/L$) and neutrophils/leukocytes (%);
- Other parameters: platelets ($10^9/L$).

Coagulation parameters will be listed and grouped as follows:

- Coagulation parameters: activated Partial Thromboplastin Time (sec) and aPTT ratio (see calculation in section 10).

Blood chemistry parameters will be listed and grouped as follows:

- Liver function: alanine aminotransferase (ALT) (IU/L), alkaline phosphatase (IU/L), aspartate aminotransferase (AST) (IU/L), total bilirubin (fraction of direct bilirubin in case > 1.25 x ULN) ($\mu\text{mol}/L$) and gamma glutamyl transferase (GGT) (IU/L), lactate dehydrogenase (LDH) (IU/L);
- Renal chemistry: creatinine ($\mu\text{mol}/L$) and urea (mmol/L);
- Electrolytes: bicarbonate, calcium, chloride, phosphorus, potassium and sodium (all electrolytes expressed in mmol/L);
- Metabolism parameters: fasting glucose (mmol/L);
- Other proteins: albumin (g/L), creatine kinase (and fraction of CK-MB if > 1.5 x ULN) (IU/L) and total protein (g/L).

Urinalysis parameters will be listed and grouped as follows:

- Planned urinalysis parameters: cylinders, erythrocytes and leucocytes.

For haematology, blood chemistry and coagulation, absolute values and changes from baseline will be described by treatment group (and overall) and measurement time.

For urinalysis, absolute values will be described by summary statistics or frequency tables by treatment group and measurement time.

For haematology, blood chemistry, coagulation and urinalysis, values higher or lower than the laboratory reference range (H, L) will be listed.

For haematology and blood chemistry, a summary table with the number and percentage of subjects with potentially clinically significant abnormal (PCSA) values (defined in section 16.2) will be generated by treatment group (and overall) and measurement time.

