13.3. Other safety parameters

13.3.1. Vital signs data

Supine systolic and diastolic blood pressure (mmHg), heart rate (beats/min) and body temperature (C°) will be measured at screening, then from D1 to D4 (pre-dose, 60min, 2h, 4h, 6h, 8h, 10h, 12h, 24h, 48h, 72h post-dose), and the discharge visit (D10 ± 2 days) (see section 16.1).

Weight will be measured at screening and the discharge visit (D10 ± 2 days).

Absolute values and changes from baseline will be described by treatment group (and overall) and measurement time.

Graphs of median ± SEM over time will be provided for changes from baseline with all treatment groups on the same graph. The median of all treatment groups will be also represented.

A summary table with the number and percentage of subjects with PCSA values (defined in section 16.2) will be generated by treatment group and measurement time.

A specific listing of subjects with PCSA values will be generated.

Values (absolute values and changes from baseline) will be listed and PCSA values will be flagged with clinical significance information.

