13.3.2. Electrocardiogram data

Supine 12-lead ECG parameters [including heart rate (beats/min), PR interval (msec), QRS duration (msec), QRS axis (deg), QTc interval (msec), Bazett QTc interval (QTcB) (msec) and Fridericia QTc interval (QTcF) (msec)] and ECG abnormalities will be recorded at screening, then on D1 (pre-dose, 2h, 4h, 6h, 8h, 12h), 24h (D2), 48h (D3), 72h (D4) post-dose and at the discharge visit (D10 ± 2 days) (see section 16.1).

Only interpretable ECGs will be analysed.

QTcB will be derived using the following formula:

$$QTcB (ms) = QT (ms) \times \sqrt{\frac{HR(bpm)}{60}}$$

Absolute values and changes from baseline (except for QRS axis in degrees and ECG abnormalities) will be described by treatment group (and overall) and measurement time.

Graphs of median ± SEM over time will be provided for changes from baseline with all treatment groups on the same graph. The median of all treatment groups will be also represented.

A summary table with the number and percentage of subjects with PCSA values (defined in section 16.2) will be generated by treatment group and measurement time.

Shift tables with the number of subjects having values lower than the lower PCSA limit (Low), normal and higher than the upper PCSA limit (High) (defined in section 16.2) according to the baseline position will be prepared by treatment group and measurement time.

A specific listing of subjects with PCSA values will be generated.

Values [absolute values/ECG abnormalities and changes from baseline (except for QRS axis in degrees)] will be listed and data out of the PCSA ranges will be flagged with clinical significance information.

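### The PCSA tables count participants only by scheduled time and from the first post-dose value, so they do not give the number per dose with any abnormality and can omit a more extreme repeat result

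*SAP*

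**What the plan says.** - **Laboratory count table (SAP 13.2).** For haematology and chemistry, the table of participants with "PCSA) values (defined in section 16.2) will be generated by treatment group (and overall) and measurement time". The bracketed addition belongs to the treatment groups, meaning a column for all groups together. It does not pool times.
- **Vital signs and ECG (SAP 13.3.1, 13.3.2).** The number and percentage of participants "with PCSA values (defined in section 16.2) will be generated by treatment group and measurement time"; the ECG section uses the same sentence. The shift tables in 13.2 and 13.3.2 are also by time. The output list in SAP 16.4 contains no any-time or worst-value PCSA table.
- **Post-dose times.** After screening, laboratory tests are at "pre-dose (D1), 24h (D2), 72h post-dose (D4), and then at the discharge visit (D10 ± 2 days"), which leaves three post-dose times. ECGs are at screening, "then on D1 (pre-dose, 2h, 4h, 6h, 8h, 12h), 24h (D2), 48h (D3), 72h (D4) post-dose and at the discharge visit", which leaves nine. Vital signs have eleven (1, 2, 4, 6, 8, 10, 12, 24, 48 and 72 h, and discharge).
- **Retests (SAP 6.3, all parameters).** "the first reliable value will be used for the measurement time after the study drug administration".
- **Where repeats come from.** For clinically significant abnormal laboratory results after dosing, protocol 9.7.6.2.3 says "testing will be repeated until the values return to normal or baseline". Protocol 9.7.3.2 has blood pressure rechecked at once after a clinically important change, and protocol 8.4 allows unscheduled visits before discharge.
- **What the tables should serve.** Protocol 10.2.10.2 promises a summary of participants with PCSA values but fixes no layout. The dose-limiting toxicity (DLT) items in protocol 7.5 count people, for example "Increase in ALT/AST ≥ 5 x ULN in 2 participants in the study".

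**The concern.** Safety is the primary objective, and laboratory values, vital signs and ECG are components of its endpoint. The natural question for each dose is how many participants ever crossed a PCSA limit, and how far. A set of by-time counts does not answer it, because two participants abnormal at different times and one participant abnormal twice produce the same table.

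The retest rule adds a second problem. If a repeat at a scheduled time is more extreme than the first reliable value, the table keeps the milder one. A repeat drawn between D4 and discharge has no row in 13.2, and 6.3 gives no rule that assigns it to one.

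The SAP already uses the per-participant unit elsewhere: 13.1 counts participants with at least one TEAE and takes the highest recorded intensity. The PCSA tables do neither. The combined item in protocol 7.5 (ALT/AST at least 3 x ULN with total bilirubin at least 2 x ULN in one participant) cannot be seen in any table, because SAP 16.2 treats each analyte separately.

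**Working it through.** The plan gives no figure to reproduce, and its sample size is not based on power. The check is what by-time counts can and cannot determine.

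**1. Bounds on the number of distinct participants.** Let c_i be the count at time i in one treatment group of n participants. Then

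max(c_i) ≤ distinct participants ≤ min(n, Σc_i).

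With n = 6 active per cohort (SAP section 4) and one abnormal participant at every post-dose time:

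| Data | Post-dose times | Σc_i | Distinct participants |
|---|---|---|---|
| Chemistry, haematology | 3 | 3 | 1 to min(6, 3) = 3 |
| ECG | 9 | 9 | 1 to min(6, 9) = 6 |
| Vital signs | 11 | 11 | 1 to min(6, 11) = 6 |

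**2. A case next to a protocol criterion.** SAP 16.2 starts the High+ grade for ALT and AST at 5 x ULN, the cut-off in the protocol 7.5 item. High+ counts of 1, 1, 0 within one treatment group give max = 1 and sum = 2, so one or two participants. The protocol item is met at two. If the two counts fall in different treatment groups, they are different people and the ambiguity disappears.

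**3. Retest example (hypothetical values).** First ALT 4 x ULN, repeat at the same scheduled time 6 x ULN. Under 6.3 the table uses 4 x ULN, which is High (3 to below 5 x ULN). The repeat would be High+ (5 to below 10 x ULN).

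**4. Any-time frequency under an assumed per-time rate.** The documents give no rate, so p is an assumption. With complete overlap (the same participants each time) the any-time rate is p. With independence over k times it is 1 − (1 − p)^k:

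| Assumed p | k = 3 (laboratory) | k = 9 (ECG) | k = 11 (vital signs) |
|---|---|---|---|
| 2 % | 5.9 % | 16.6 % | 19.9 % |
| 5 % | 14.3 % | 37.0 % | 43.1 % |
| 10 % | 27.1 % | 61.3 % | 68.6 % |

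At p = 5 %, for instance, 1 − 0.95^3 = 0.143 and 1 − 0.95^11 = 0.431. These figures only illustrate how far apart the two readings can lie. Repeated measurements in one person are unlikely to be independent, and in a group of 6 the smallest non-zero proportion is already 1/6 = 17 %.

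**The case against.** The strongest reply is that the information is not lost. SAP 6.2 sorts all safety listings by treatment group, subject and time. Listings of participants with PCSA values are planned for laboratory, vital-sign and ECG data, and with 4 x 8 = 32 participants a reader can count by eye. This largely stands: what is missing is a printed count. But the SAP does not say that the listings include repeat or unscheduled results.

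Second, clinically relevant abnormalities become adverse events under protocol Appendix 2 and are then counted per participant in SAP 13.1. This also narrows the gap. It does not close it, because AE recording rests on the investigator's judgement and AE terms do not carry the numerical limits of SAP 16.2.

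Third, repeats rarely change a table. Protocol 9.7.6.2.3 covers only clinically significant laboratory results, and a repeat matters only if it crosses a limit or grade that the first value did not. That is right, so the tables *can* omit the worst value; they do not do so as a rule.

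A reader might go further and infer that DLT surveillance is weakened. The documents do not support this. Under protocol 7.4 and 7.5 those decisions are taken during the trial by the Safety Review Committee from the Investigator Safety Report, and the final tables play no part. Nor do all DLT items count events at any time: the aPTT item is fixed at 24 h, which suits a by-time table.

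**Conclusion.** The concern holds as a gap in final safety reporting. As written, no PCSA table gives the number of participants per dose with at least one abnormality, and the first-value rule can under-grade or leave out a participant whose extreme value came on a repeat or between visits. This applies mainly to laboratory data, where repeat testing is mandated and there are only three post-dose times.

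The size depends on the data. There is no ambiguity from the layout when a parameter has no PCSA or is abnormal at one time only. With 1/6 at every time it spans 1 to 3 of 6 participants for laboratory data and 1 to 6 of 6 for ECG and vital signs. The percentages in the working rest on assumed rates and should not be read as expected incidences. It would also be wrong to infer that the worst values vanish from the report: the listings may show them, but the SAP does not say so.

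**What to change.** - In SAP 13.2, 13.3.1 and 13.3.2, add one row per parameter, and per grade where graded: number (%) of participants with at least one PCSA at any post-dose time, by treatment group, using the worst reliable value including repeat and unscheduled results.
- Add one row for ALT/AST ≥ 3 x ULN with total bilirubin ≥ 2 x ULN in the same participant.
- State that the PCSA listings include repeat and unscheduled values.
- Keep 6.3 unchanged for the by-time summaries.
- While doing this, settle aPTT: SAP 16.2 sets PCSA limits for its value and ratio, but 13.2 and 16.4 plan no PCSA count table for coagulation, so the new row has nowhere to go.

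The cost is SAP wording and a few table rows from data already collected. The SAP has already been supplemented by two appendices, so a route exists. There is one small downside: participants with abnormal results are sampled more often and so have more chances of an extreme value. A footnote to the new rows should say this.

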13.3. Other safety parameters

13.3.1. Vital signs data

Supine systolic and diastolic blood pressure (mmHg), heart rate (beats/min) and body temperature (C°) will be measured at screening, then from D1 to D4 (pre-dose, 60min, 2h, 4h, 6h, 8h, 10h, 12h, 24h, 48h, 72h post-dose), and the discharge visit (D10 ± 2 days) (see section 16.1).

Weight will be measured at screening and the discharge visit (D10 ± 2 days).

Absolute values and changes from baseline will be described by treatment group (and overall) and measurement time.

Graphs of median ± SEM over time will be provided for changes from baseline with all treatment groups on the same graph. The median of all treatment groups will be also represented.

A summary table with the number and percentage of subjects with PCSA values (defined in section 16.2) will be generated by treatment group and measurement time.

A specific listing of subjects with PCSA values will be generated.

Values (absolute values and changes from baseline) will be listed and PCSA values will be flagged with clinical significance information.

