3.4. Visits

For cohorts from A to D, the study will include the following visits (see section 16.1.1):

	Cohorts A, B and C	Cohort D
Screening	from Day-28 to Day -2 (Visit V1)	
Randomisation	Day 1 (pre-dose, Visit V3)	
Treatment period	from Day -1 (Visit V2) to Day 5 (Visit V7)	from Day -1 (Visit V2) to Day 7 (Visit V8)
Discharge visit	Day 10 (\pm 2 days) (Visit V8)	Day 10 (\pm 2 days) (Visit V9)
Extra ambulatory visits for ADA analysis	Day 30 (\pm 3 days) (1 month, Visit V9) Day 90 (\pm 7 days) (3 months, Visit V10) Day 180 (\pm 7 days) (6 months, Visit V11)	Day 30 (\pm 3 days) (1 month, Visit V10) Day 90 (\pm 7 days) (3 months, Visit V11) Day 180 (\pm 7 days) (6 months, Visit V12)

All participants will receive a single intravenous dose of Ir-CPI/Placebo at Day 1, given as a 6-hour infusion.

4. Sample Size

The number of participants is not based on statistical power considerations. A sample size of 8 participants per panel (i.e., 6 active and 2 placebo) was chosen based on the design of similar SAD studies and is considered adequate to provide an initial assessment of the safety and tolerability profile of Ir-CPI.

5. Changes to the planned analysis from protocol

The following changes are added compared to the planned analysis detailed in the study protocol:

- Addition of the Screened set (defined as all of the subjects having signed an informed consent form) (see section 7.1).
- Orthostatic hypotension and abnormal HR will not be derived because there are not standing vital signs measured during the study.
- Only the Part 1 was performed with 4 cohorts (A, B, C and D) (instead of Part 1 with 5 cohorts and Part 2 with 3 cohorts) and with the following dose modifications discussed during SRC meetings (see minutes of these meetings):
 - Cohort A: Ir-CPI 1.5 mg/kg;
 - Cohort B: Ir-CPI 3 mg/kg;
 - Cohort C: Ir-CPI 6 mg/kg;
 - Cohort D: Ir-CPI 9 mg/kg.
- In exploratory objectives, the investigation of the ADA capability to neutralize drug activity was not performed, and the assessment of the PK of Ir-CPI in urine was also not done.
- Addition of statistical analysis of AUC_{0-96h} and AUC_{0-last} (see section 9.2.2).

6. Statistical considerations

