6.2. Descriptive statistics and data listings

Descriptive statistics will be supplied according to the nature of the criteria:

- Quantitative variable: sample size, arithmetic mean, standard deviation (SD), standard error of the mean (SEM), minimum, median and maximum, and [quartiles if necessary with geometric mean, arithmetic and geometric coefficients of variation (CV), and quartiles for PK parameters].
- Qualitative variable: sample size, absolute and relative frequencies per class. Percentages will be provided with one decimal place.

If the sample size of one treatment group is less than or equal to 2, only the number of observed values, the minimum and the maximum will be presented for quantitative variables and the percentage of subjects will not be presented for qualitative variables.

Unless specified otherwise, the calculation of percentages will be based on the number of observed values. Therefore, counts of missing values will be included in the denominator and displayed as a separate category if any.

Data will be organised by treatment group:

- Pooled Placebo;
- Ir-CPI 1.5 mg/kg;
- Ir-CPI 3 mg/kg;
- Ir-CPI 6 mg/kg;
- Ir-CPI 9 mg/kg.

All demographic, pharmacokinetics, pharmacodynamics, safety and tolerability listings will be sorted by treatment group, subject and measurement time if applicable.

All listings containing an evaluation date will display the study day defined as the day relative to the administration of study drug:

- Study day 1 will be defined as the day of the study product administration date;
- Study day -1 will be defined as the day prior to the study product administration date;
- There will be no study day 0.

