9.2.2. Plasma pharmacokinetic analysis

The plasma pharmacokinetic analysis will be performed on the PKS set.

Subjects receiving placebo will not be included in the summary and analysis of PK parameters. Listings with plasma concentrations (including dates and times of PK blood sampling) and PK parameters will be provided by treatment group and subject. These listings will be generated for all subjects with an available PK profile (complete or incomplete), including those who are excluded from the PKS.

Plasma concentrations and PK parameters of Ir-CPI including descriptive statistics will be presented in tables separately for each treatment group.

Individual plasma concentration versus time profiles of Ir-CPI will be presented graphically on linear and log/linear coordinates for each subject.

The graph of arithmetic mean \pm SEM over time will be provided for plasma concentration of Ir-CPI on linear and log/linear coordinates with all treatment groups (cohorts A, B, C and D) on the same graph. A reference line corresponding to the lowest C_{max} values at the NOAEL (No Observed Adverse Effect Level), i.e. 53.7 μ g/mL will be added on the graph of mean and individual concentration-time profiles on log/linear coordinated only.

A graph of arithmetic mean \pm SEM with min-max curves over time will be provided for plasma concentration of Ir-CPI for each treatment group on linear coordinates.

Individual plasma concentration-time profiles (spaghetti plots) of Ir-CPI will also be presented for each treatment group on linear coordinates.

Box whisker plots will be generated for the comparison of C_{max} , AUC_{0-6h} , AUC_{0-96h} , AUC_{0-last} and AUC_{0-inf} .

The linear dose-proportionality of the maximum concentration (C_{max}) and the areas under the concentration-time curve (AUC_{0-6h} , AUC_{0-96h} , AUC_{0-last} and AUC_{0-inf}) will be assessed for Ir-CPI using an exponential regression model ("power model") that measures the degree of non-linear proportionality [2]. The PK parameter and dose values will be logarithmically

transformed prior to analysis and evaluated using a 1-factor analysis of variance (ANOVA) including log (dose) as fixed effect and subject as random effect.

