14.3.3.2.5	Listing of subjects presenting PCSA values – Safety set
14.3.3.3	Coagulation
14.3.3.3.1	Summary statistics – Safety set
14.3.3.3.2	Listing of subjects presenting abnormal values – Safety set
14.3.3.4	Urinalysis
14.3.3.4.1	Summary statistics – Safety set
14.3.3.4.2	Listing of subjects presenting abnormal values – Safety set
14.3.4	Other safety parameters
14.3.4.1	Vital signs data
14.3.4.1.1	Summary statistics – Safety set
14.3.4.1.2	Graphs of vital signs (median \pm SEM) over time (changes from baseline) – Safety set
14.3.4.1.3	Number and percentage of subjects with PCSA values – Safety set
14.3.4.1.4	Listing of subjects presenting PCSA values – Safety set
14.3.4.2	Electrocardiogram data – Standard 12-lead ECG parameters
14.3.4.2.1	Summary statistics – Safety set
14.3.4.2.2	Graphs of ECG parameters (median \pm SEM) over time (changes from baseline) – Safety set
14.3.4.2.3	Number and percentage of subjects with PCSA values – Safety set
14.3.4.2.4	Shift tables (PCSA values) – Safety set
14.3.4.2.5	Listing of subjects presenting PCSA values – Safety set
14.3.4.3	Physical examination
14.3.4.3.1	Listing of subjects presenting abnormal results – Safety set
14.3.4.4	Telemetry monitoring
14.3.4.4.1	Summary statistics – Safety set
14.3.4.4.2	Listing of subjects presenting abnormal results – Safety set
14.3.4.5	Occult blood in faeces
14.3.4.5.1	Summary statistics – Safety set
14.3.4.5.2	Listing of subjects presenting abnormal results – Safety set

NUMBER	TITLE
14.3.4.6	Exposure to tick bites – Safety set
16.1	STUDY INFORMATION
16.1.7	Randomisation scheme and codes (subject identification and treatment assigned) – Randomised set
16.1.9	Documentation of statistical methods
16.1.9.1	Statistical analysis plan (integrated by the medical writer during the creation of the appendices of the clinical study report)
16.1.9.2.	ANOVA: Analysis of dose-proportionality for C _{max} , AUC _{0-6h} , AUC _{0-96h} and AUC _{0-inf} for Ir-CPI – Pharmacokinetic set
16.2	SUBJECT DATA LISTINGS
16.2.1	Subject disposition
16.2.1.1	Discontinued subjects – Included set
16.2.1.2	Subject disposition and analysis sets – Included set
16.2.1.3	End of study status – Included set
16.2.1.4	Subject visit dates – Included set
16.2.1.5	Screen failures – Screened set
16.2.2	Protocol deviations
16.2.2.1	Deviations relating to inclusion/exclusion criteria – Randomised set
16.2.2.2	Other deviations – Randomised set
16.2.3	Subjects excluded from analysis sets – Randomised set

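### The vital-sign and ECG change-from-baseline graphs draw the standard error of the mean around a median, so the bars do not describe the plotted point

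*SAP*

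**What the plan says.** SAP 13.3.1, on vital signs: "Graphs of median ± SEM over time will be provided for changes from baseline", with every treatment group on one graph. SAP 13.3.2 gives the identical instruction for the ECG parameters. Both sections add that a median across all treatment groups will be drawn as well. In the output list (SAP 16.4), the titles of 14.3.4.1.2 (vital signs) and 14.3.4.2.2 (ECG) both pair the median with SEM.

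The abbreviation is fixed in SAP 6.2, where the descriptive statistics for quantitative variables include "standard error of the mean (SEM), minimum, median and maximum". No section gives SEM another meaning for the safety graphs.

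Elsewhere, SEM is plotted only with a mean: plasma concentrations (SAP 9.2.2), aPTT ratio and FXI/FXII inhibition (SAP 10), and the biomarker graphs (output 14.2.3.2.2). The protocol does not specify the safety graphs, so the SAP is the only source for them.

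**The concern.** An error bar is read as a statement about the point it surrounds. Here the point is a median and the bar is the standard error of a different statistic. Because the pairing appears in two sections and two output titles, and both sections also ask for an all-groups median, a programmer following the SAP would produce it.

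Safety and tolerability is the primary objective. In section 14.3 of the output list these two outputs are the only graphs; the rest are tables and listings. They overlay all treatment groups, with 11 post-dose times for vital signs and 9 for ECG, counting the discharge visit. What is at stake is whether the only pictures of blood pressure, heart rate and QTc change show their precision correctly.

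**Working it through.** The plan states no figure on this point, so there is nothing to reproduce. The check sizes the mismatch.

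**Inputs from the documents**
- Each panel has 6 active and 2 placebo participants (SAP 4), and four panels were run (SAP 3.2).
- Placebo is pooled (SAP 6.2), so n = 6 per active dose group and 4 × 2 = 8 for placebo.
- SEM = s/√n, the standard error of the mean (SAP 6.2).

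**Assumption.** The documents give no distribution for the changes from baseline. The shapes below only show a range.

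**Step 1: standard error of the median relative to the true SEM (σ/√n), by simulation**

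| Assumed shape | n = 6 | n = 8 |
|---|---|---|
| Normal | 1.13 | 1.16 |
| Laplace | 0.89 | 0.86 |
| t, 3 df | 0.79 | 0.78 |
| Lognormal, sigma 1 | 0.65 | 0.62 |

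For normal data the large-sample limit is √(π/2) = 1.253, so values of 1.13 and 1.16 at small n are plausible.

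**Step 2: bar length under normality.** A bar of one SEM falls short of the standard error of the median by 1 − 1/1.13 = 0.115 (about 12%) at n = 6 and by 1 − 1/1.16 = 0.138 (about 14%) at n = 8. Median ± SEM then contains the true median in about 58% of samples at either size. Mean ± SEM contains the true mean in about 64% (n = 6) and 65% (n = 8).

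**Step 3: the comparison standard matters.** A drawn bar uses the sample SD, which on average lies below σ in small samples. Against the average drawn bar, the normal-case shortfall is about 16% to 17%. For a lognormal with sigma 0.8, the ratio to the true SEM is 0.80 (n = 6) and 0.78 (n = 8), but the ratio to the average drawn bar is 0.98 and 0.93. The average bar is then only 1/0.98 − 1 = 2% to 1/0.93 − 1 = 8% too long.

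**Step 4: illustration with n = 6 (invented values).** Take changes of −2, −1, 0, 1, 2 and 30.
- Median = (0 + 1)/2 = 0.5; mean = 30/6 = 5.0.
- Squared deviations from the mean: 49 + 36 + 25 + 16 + 9 + 625 = 760.
- s = √(760/5) = 12.33; SEM = 12.33/√6 = 5.03.
- The bar runs from 0.5 − 5.03 = −4.53 to 0.5 + 5.03 = 5.53.

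Replace 30 by 3. The median is still 0.5, the squared deviations sum to 17.5, s = √(17.5/5) = 1.87, and SEM = 1.87/√6 = 0.76. One value changes the bar from 5.03 to 0.76 while the plotted point does not move.

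**The case against.** The strongest reply is that nothing depends on these bars, and most of it stands.
- No test, threshold or stopping rule uses them. Dose escalation rested on the Investigator Safety Report and on blinded PK and PD data (Protocol 7.4).
- The summary tables give n, mean, SD, SEM, median, minimum and maximum, so mean ± SEM can be recovered exactly. PCSA tables and listings, ECG shift tables and individual listings are untouched.
- The output titles say what is drawn.
- Under normality the SEM estimate itself has a coefficient of variation of about 32% at n = 6 and 27% at n = 8, more than the mismatch.

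This limits the consequence but does not make the pairing correct. Sampling noise and a wrong target are separate faults, and an accurate label does not tell a reader how to convert the bar.

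Two stronger readings are tempting. A reader might infer that bars are about 25% too long when data are skewed. That comes from 1/0.80 = 1.25 for a lognormal with sigma 0.8, measured against the population SD. The documents support neither that shape nor that sigma, a strictly positive lognormal is an odd model for signed changes, and against the average drawn bar the excess is 2% to 8%. A reader might also infer that the bars will decide whether a dose separates from placebo. No section plans such a comparison, and SAP 4 says: "The number of participants is not based on statistical power considerations".

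**Conclusion.** The specification is wrong as written for two outputs, 14.3.4.1.2 and 14.3.4.2.2, and the sections that define them. Under normality the bars are about 12% to 14% too short relative to the true SEM. With skewed or heavy-tailed changes the direction can reverse, and the amount cannot be fixed without an assumed distribution, so a reader cannot apply a standard correction.

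The consequence is small. A reader might conclude that the safety conclusions are at risk or that SEM bars are misused throughout the SAP. Neither follows: the numerical safety outputs are unaffected, and the PK, PD and biomarker graphs pair SEM with a mean. It is worth correcting because these are the only planned safety graphs and the correction is cheap.

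**What to change.** Amend SAP 13.3.1, SAP 13.3.2 and both output titles in SAP 16.4, using one of two matched pairs:

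- **(a) Mean ± SEM**, as in the PK and PD graphs. The sentence in each section that adds an all-groups median must then refer to the mean.
- **(b) Median with Q1 to Q3.** The reporting table in SAP 14 reserves the quartiles for PK parameters, so its footnote must be extended to vital-sign and ECG parameters. SAP 6.2 already allows quartiles where necessary. The all-groups median can stay.

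Either option means edits to two sections and two titles, plus the dependent sentences in (a) or the table footnote in (b), and a change to the plotting code. Option (b) also adds quartiles to the summary output for these parameters. No new data or analysis set is needed. If the graphs already exist, re-plot them or add a footnote in the study report stating that the bars are standard errors of the mean and not of the median.
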